APPENDIX V

DIARRHEA MANAGEMENT GUIDELINES

Presented in the sections below are the recommended guidelines for the management of diarrhea in patients receiving lapatinib-based therapy; these guidelines were derived from the recommendations published by the ASCO panel (Benson, 2004).

Early identification and intervention is critical for the optimal management of diarrhea. A patient's baseline bowel patterns should be established so that changes in patterns can be identified while patient is on treatment.

It is strongly recommended to give patients receiving lapatinib-based therapy a prescription of loperamide with instructions to start loperamide at the onset of diarrhea as per the recommendations outlined below.

Patients should be instructed to first notify their physician/healthcare provider at onset of diarrhea of any severity.

An assessment of frequency, consistency and duration as well as knowledge of other symptoms such as fever, cramping, pain, nausea, vomiting, dizziness and thirst should be taken at baseline. Consequently patients at high risk of diarrhea can be identified. Patients should be educated on signs and symptoms of diarrhea with instructions to report any changes in bowel patterns to the physician.

It is recommended that patients keep a diary and record the number of diarrhea episodes and its characteristics. They should also include information on any dietary changes or other observations that may be useful in the evaluation of their diarrhea history.

If patients present with diarrhea of any Grade, check they are taking lapatinib correctly, i.e. single daily dose, rather than splitting it through the day. Obtain information on food (solid and liquid) and over the counter (OTC) medication, including herbal supplements, taken during the lapatinib treatment period.

Definitions

Define diarrhea compared to baseline (Table 1).

Table 1

Adverse Event Grade, CTCAE v. 4	Diarrhea
1	Increase of <4 stools/day over baseline; mild increase in ostomy output compared to baseline
2	Increase of 4-6 stools/day over baseline; moderate increase in ostomy output compared to baseline;
3	Increase of ≥7 stools/day over baseline; incontinence; hospitalization indicated; severe increase in ostomy output compared to baseline; limiting self care activities of daily living (ADL)
4	Life-threatening consequences; urgent intervention indicated
5	Death

APPENDIX V (Continued)

Uncomplicated diarrhea is considered mild-to-moderate and defined as CTCAE v. 4 grade 1 or 2 with no complicating signs or symptoms.

Complicated diarrhea is severe and defined as any CTCAE v. 4 grade 3 or 4 diarrhea, or grade 1 or 2 with one or more of the following signs or symptoms:

- Moderate to severe abdominal cramping
- Nausea/vomiting \geq Grade2
- Decreased performance status
- Fever
- Sepsis
- Neutropenia
- Frank bleeding (red blood in stool)
- Dehydration

Management Guidelines for Patients Receiving Lapatinib Alone or as Combination Therapy

A) Uncomplicated Diarrhea

I. CTCAE Grade 1

NOTE: Patient should be instructed to start supportive care immediately at the first episode of diarrhea (i.e., unformed stool) and call their physician.

1. Administer loperamide
 - a. Initial dose 4mg followed by 2mg after every unformed stool. Re-evaluate after 24 hours, if:
 - i. Diarrhea is resolving:
 - Continue loperamide treatment at 2mg dose after every unformed stool until diarrhea free (i.e., $<$ Grade 1/bowel patterns returned to baseline) for 12 hours.
 - If diarrhea recurs, re-initiate loperamide treatment as needed to maintain normal bowel patterns
 - ii. Diarrhea is not resolving:
 - Administer loperamide at 2mg every 4 hours for the next 24 hour. Re-evaluate after 24 hours. If diarrhea is resolving, administer loperamide at 2mg after every unformed stool until diarrhea free (i.e., $<$ Grade 1/bowel patterns returned to baseline) for 12 hours. If diarrhea is not resolving continue loperamide treatment at 2mg every 4 hours and re-evaluate every 24 hours.
 - b. If Grade 1 diarrhea persists for more than 1 week with loperamide treatment, consider treatment with second-line agents (octreotide, budesonide or tincture of opium).
2. Dietary modifications which are essential in the management of diarrhea include the following recommendations (American Cancer Society; National Cancer Institute):
 - a. Stop all lactose containing products and eat small meals
 - b. Avoid spicy, fried and fatty foods, raw vegetables and other foods high in fiber
 - i. Eat foods low in fiber (i.e., lean meat, rice, skinless chicken or turkey, fish, eggs, canned or cooked skinless fruits, cooked/pureed vegetables)
 - c. Avoid caffeine and alcohol as they can irritate the bowel and increase motility
 - d. Hydration: Drink 8-10 large glasses of clear liquids a day (e.g., water, electrolyte drink).
 - i. Avoid acidic drinks such as tomato juice and fizzy soft drinks
 - e. Supplement diet to include foods rich in potassium (e.g., bananas, potatoes, and apricots) , evaluate their impact on diarrhea due to the fiber content (e.g., apricots)

APPENDIX V (Continued)

3. Continue with study treatment (i.e. lapatinib-based treatment)
Continue with supportive care until diarrhea has resolved (diarrhea free for 12 hours/bowel pattern return to baseline). Once diarrhea has resolved, the patient can begin to gradually re-introduce foods from their normal diet.

If diarrhea recurs following stopping of loperamide treatment, resume loperamide treatment at the dose and schedule recommended above and re-introduce diet modifications. Continue with study treatment.

If grade 1 diarrhea persists for ≥ 2 weeks, refer to the management guidelines for persistent grade 2 diarrhea.

II. CTCAE Grade 2

NOTE: Patient should be instructed to call physician at first episode of diarrhea and start supportive care immediately

1. Administer loperamide
 - a. Initial dose 4mg followed by 2mg every 4 hours or after every unformed stool. Re-evaluate after 24 hours. If:
 - i. Diarrhea is resolving, continue loperamide treatment at 2mg dose after every unformed stool until diarrhea free (i.e., $<$ Grade 1/bowel patterns returned to baseline) for 12 hours
 - If diarrhea recurs, re-initiate loperamide treatment as needed to maintain normal bowel patterns
 - ii. Diarrhea is not resolving, consider loperamide dose of 2mg every 2 hours for 24 hours. If Grade 2 diarrhea persists after total of 48 hours of loperamide treatment, start second-line agents (octreotide, budesonide or tincture of opium).
 - Consider performing stool work-up, CBC, electrolytes and other tests as appropriate
2. Dietary modifications which are essential in the management of diarrhea include the following recommendations (American Cancer Society; National Cancer Institute):
 - a. Stop all lactose containing products and eat small meals
 - b. Avoid spicy, fried and fatty foods, bran, raw vegetables and other foods high in fiber
 - i. Eat foods low in fiber (i.e., lean meat, rice, skinless chicken or turkey, fish, eggs, canned or cooked skinless fruits, cooked/pureed vegetables)
 - c. Avoid caffeine and alcohol as they can irritate the bowel and increase motility
 - d. Hydration: Drink 8-10 large glasses of clear liquids a day (e.g., water, electrolyte drink).
 - i. Avoid acidic drinks such as tomato juice and fizzy soft drinks
 - e. Supplement diet to include foods rich in potassium (e.g., bananas, potatoes, and apricots), evaluate their impact on diarrhea due to the fiber content (e.g., apricots)
3. Continue with study treatment (i.e., lapatinib-based treatment)
Continue with supportive care until diarrhea has resolved (diarrhea free for 12 hours/bowel pattern return to baseline). Once diarrhea has resolved, the patient can begin to gradually re-introduce foods from their normal diet. Refer to Section IV "Recurrent Diarrhea" for study treatment guidelines.

If diarrhea recurs following stopping of loperamide treatment, resume loperamide treatment at the dose and schedule recommended above and re-introduce diet modifications.

APPENDIX V (Continued)

- III. Persistent (≥ 3 days/72 hours) Grade 2 Diarrhea:** hold lapatinib and chemotherapy (if applicable) until diarrhea resolves ($<$ Grade 1/return to baseline bowel pattern). If supportive care measures are ineffective, consider the following:
1. If supportive care measures and the interruption of study treatment (i.e., lapatinib and if applicable chemotherapy) are ineffective in treating persistent Grade 1 or Grade 2 diarrhea, perform stool work-up, CBC, electrolytes and other tests as appropriate, consider consulting with a gastrointestinal (GI) specialist.
 - a. After diarrhea resolves (\leq Grade 1), resume treatment with lapatinib and chemotherapy (if applicable).
- IV. Recurrent Diarrhea (more than 1 occurrence of Grade 2 diarrhea):** once the 2nd occurrence of grade 2 diarrhea resolves to \leq grade 1, consider reducing the dose of lapatinib by 250mg or 1 tablet, unless the lapatinib dose already had been reduced to 750mg. No further dose reduction is recommended for patients taking lapatinib at 750mg.
1. Consider a dose reduction for chemotherapy (if applicable)

B) Complicated Diarrhea

- I. CTCAE, v 4 grade 3 or Grade 1 or 2 with complicating features (severe cramping, severe nausea/vomiting, decreased performance status, fever, sepsis, Grade 3 or 4 neutropenia, frank bleeding, dehydration)**
1. Patient **must** call physician immediately for any complicated severe diarrhea event
 2. If loperamide has not been initiated, initiate loperamide immediately: Initial dose 4mg followed by 2mg every 2 hours or after every unformed stool
 3. Refer to the dietary modification recommendations for Grade 1 and Grade 2 uncomplicated diarrhea
 4. For dehydration use intravenous fluids as appropriate, if patient presents with severe dehydration administer octreotide
 5. Perform stool work-up, CBC, electrolytes and other tests as appropriate
 6. Administer antibiotics as needed (example fluoroquinolones), especially if diarrhea is persistent beyond 24 hours or there is fever or Grade 3-4 neutropenia
 7. Hold lapatinib and chemotherapy (if applicable) until symptoms resolve to \leq Grade 1 and reintroduce lapatinib at a reduced dose (unless dose had been reduced to 750mg, contact medical monitor for further guidance)
 - a. Consider a dose reduction for chemotherapy (if applicable)
 8. Supportive care and other interventions should be continued until diarrhea free (i.e., $<$ Grade 1/bowel patterns returned to baseline) for 24 hours
 9. Intervention may require hospitalization for patients most at risk for life threatening complications

[figure not shown]

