7.4.6.4 Gastrointestinal

Experience thus far suggests that when lapatinib is used as monotherapy most diarrhea presents as uncomplicated CTCAE v. 4 grade 1 or 2 (G1 54%, G2 20%, G3 15%, G4<1%). In rare cases, diarrhea can be debilitating, and potentially life threatening if accompanied by dehydration, renal insufficiency, and/or electrolyte imbalances. Standardized and universal guidelines have been developed by an American Society of Clinical Oncology (ASCO) panel for treating chemotherapy-induced diarrhea (Benson, 2004). Early identification and intervention is critical for the optimal management of diarrhea. A patient's baseline bowel patterns should be established so that changes in patterns can be identified while the patient is on treatment. See Section 7.7.5 for management of nausea and/or vomiting and Appendix V for diarrhea management guidelines.

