7.6.1.5 Other Adverse Events

- Mucositis: Significant mucositis from radiation and cisplatin is expected and will not be an indication for cisplatin dose modification. No cisplatin dose reductions will be made.

- Ototoxicity: For new clinical hearing loss not requiring a hearing aid or for tinnitus that interferes with activities of daily living, treat at 50% dose reduction. For hearing loss requiring a hearing aid, discontinue cisplatin. Continue RT and lapatinib/placebo.
- If the physician is unsure about the severity of the hearing loss, an audiogram is encouraged.

7.6.1.6 If the second dose of cisplatin is delayed more than 21 days because of hematologic or renal adverse events, that dose will be omitted.

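### Appendix V gives two conflicting definitions of complicated grade 1-2 diarrhea, and its chemotherapy holds are not reconciled with the cisplatin rules in Section 7.6.1

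*Combined protocol and SAP*

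**What the plan says.** The definitions part of Appendix V states: "Complicated diarrhea is severe and defined as any CTCAE v. 4 grade 3 or 4 diarrhea, or grade 1 or 2 with one or more". Eight features are then listed, and the first is "Moderate to severe abdominal cramping". The list also sets nausea/vomiting at grade 2 or above and names neutropenia without a grade.

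The management part has its own list. The heading of B) I covers grade 3 diarrhea and also a second group, described as: "Grade 1 or 2 with complicating features (severe cramping, severe nausea/vomiting, decreased performance status, fever, sepsis, Grade 3 or 4 neutropenia, frank bleeding, dehydration". Item 7 under it says "Hold lapatinib and chemotherapy (if applicable) until symptoms resolve to" grade 1 or less. Lapatinib is then restarted at a lower dose, and a chemotherapy reduction is to be considered. For uncomplicated grade 1 or 2 diarrhea, A) I and A) II say to continue study treatment.

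A) III (persistent grade 2) also holds lapatinib and chemotherapy, and B) II (grade 4) also holds chemotherapy. A) IV asks for a chemotherapy reduction to be considered when grade 2 diarrhea recurs.

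Section 7.6.1, the cisplatin modification section, covers day 29. It has rules for neutropenia, thrombocytopenia, neurotoxicity, renal function, mucositis and ototoxicity, but none for diarrhea and no reference to Appendix V. Its delay limit in 7.6.1.6 reads: "If the second dose of cisplatin is delayed more than 21 days because of hematologic or renal adverse events, that dose will be omitted". The reference to Appendix V stands in Section 7.7, on lapatinib/placebo adverse events.

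**The concern.** The two lists decide between opposite actions. A patient whose features meet the first list but not the second is complicated by definition, yet falls outside the heading that says what to do about complicated diarrhea. One site may continue treatment, and another may hold both drugs and restart lapatinib/placebo at a lower dose. Both can point to the protocol.

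Cisplatin is the only chemotherapy in the regimen, so the chemotherapy wording in Appendix V can mean nothing else during concurrent treatment. Someone who reads only Section 7.6.1 would not know that diarrhea can hold cisplatin. Someone who reads only Appendix V would not know how long a dose may be delayed before it is dropped.

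Two things are at stake. One is consistent handling of patients with the same symptoms. The other is compliance with planned treatment, a secondary endpoint (13.2.4) compared by Fisher's exact test (13.6). It is supported by the chemotherapy review in Section 7.8, which grades each case from per protocol to unacceptable deviation. That review has no single rule against which to score a diarrhea hold.

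**Working it through.** The plan gives no figure on this point, so the check is mainly a comparison of texts.

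**Step 1: the two lists.**

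| Feature | Definitions list | Heading of B) I |
|---|---|---|
| Cramping | moderate or severe | severe |
| Nausea/vomiting | grade 2 or above | severe |
| Neutropenia | no grade stated | grade 3 or 4 |
| Performance status, fever, sepsis, bleeding, dehydration | listed | listed, same severity |

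Three of eight features differ and five agree. Each difference runs the same way: the list that carries the action is narrower.

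**Step 2: patients on whom the lists disagree.** Take grade 1 diarrhea with moderate cramping. It is complicated under the definitions list, so the hold applies. Under the heading of B) I it is not, so A) I applies and treatment continues. Grade 2 nausea does the same if severe is read as above grade 2. For neutropenia, take an absolute neutrophil count of 1,300, which is below the entry limit of 1,500 in Section 3.1.6.1. With grade 1 diarrhea this is arguably a hold under the definitions list. Section 7.6.1.1 holds cisplatin only below 1,200.

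**Step 3: resolution grade.** A) III holds until diarrhea is below grade 1 or at baseline, but its sub-item resumes treatment at grade 1 or less. A patient left with grade 1 diarrhea is covered by both statements. B) I item 7 uses grade 1 or less.

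**Step 4: delay limit.** A diarrhea hold ends at a resolution grade. The 21-day omission rule is confined to hematologic and renal causes. For those causes the limit falls on day 29 + 21 = day 50. Radiation starts on day 8 and runs 42 days, so it ends on day 8 + 42 - 1 = day 49. For diarrhea, nothing says whether a dose delayed beyond that point is given or omitted. Section 7.2.1 adds only that cisplatin may be held when radiation is held for more than 2 days.

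**Step 5: scale, under assumptions.** Section 7.4.6.4 gives these diarrhea rates for lapatinib alone: "G1 54%, G2 20%, G3 15%, G4<1" percent. The allocation ratio is not stated, and I assume 1:1.

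- Patients per arm: 128/2 = 64 analyzable, or 142/2 = 71 accrued.
- Grade 1-2 rate: 54% + 20% = 74%.
- Lapatinib-arm patients with grade 1-2 diarrhea: 0.74 × 64 = 47.4, and 0.74 × 71 = 52.5.
- Share meeting the first list but not the second: the documents give none, and I assume 5% to 30%.
- Low end: 0.05 × 47.4 = 2.4. High end: 0.30 × 52.5 = 15.8.

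That is about 2 to 16 patients classified differently. It is not a count of cisplatin doses changed. Cisplatin is due only on days 8 and 29, so a hold touches it only if the diarrhea and the disputed feature are present then.

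**The case against.** The strongest reply is that Appendix V is labelled recommended guidance, does not name cisplatin, and only asks that a chemotherapy reduction be considered. All of that is correct. But the hold in item 7 is worded as an instruction, and guidance that gives two answers still needs one. Figure 1, the algorithm to which Appendix V refers, cannot be seen in the available text. It may follow either list, but it cannot remove the conflict between the two written ones.

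The neutropenia difference is also partly moot for cisplatin. On day 29 a count below 1,200 holds it under Section 7.6.1.1 whichever list is used.

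Some stronger readings are tempting, and the documents do not support them:

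- A reader might infer that diarrhea-driven cisplatin changes confound the PFS comparison. They arise after randomization and belong to the effect of assignment. The ITT log-rank test in Section 13.6.4 is not biased by them. They bear on how a result is interpreted.
- A reader might infer that the two definitions themselves create a difference by arm. The same text applies to both blinded arms. A difference would come from more diarrhea on lapatinib, which is plausible, and would remain under a single definition that still held chemotherapy. No placebo or chemoradiation rate is given to size it.
- A reader might infer that a diarrhea hold is open-ended. It has a resolution grade; what is missing is a maximum delay.
- A reader might count each affected day-29 dose as half the planned cisplatin lost. Appendix V delays a dose; it does not omit it. The 88% two-cycle figure in Section 1.1 comes from an earlier trial and measures nothing here.

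**Conclusion.** The concern holds as an internal contradiction. Appendix V has two lists of complicating features that differ on three of eight items and lead to opposite actions. It also gives two thresholds for ending a hold in persistent grade 2 diarrhea. No readable part of the protocol reconciles either point. Separately, its chemotherapy holds have no counterpart and no delay limit in Section 7.6.1.

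The consequence is inconsistent holding of study drug, and possibly of cisplatin, between sites, with inconsistent scoring of the treatment-compliance endpoint. The range of 2 to 16 reclassified patients rests on 1:1 allocation, on monotherapy diarrhea rates carrying over, and on an assumed 5% to 30% overlap. It should be read only as an order of magnitude. The 69-event design and the test of PFS are unaffected. This should be corrected, but it does not threaten the primary analysis.

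**What to change.** The sponsor must reconcile these passages; which clinical rule applies is the sponsor's choice.

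1. In Appendix V, keep one list of complicating features with one severity for each, refer to it from B) I, and check that Figure 1 agrees.
2. In A) III, state one resolution threshold for ending a hold and resuming treatment.
3. Reconcile Appendix V with Section 7.6.1 on whether and how diarrhea affects cisplatin, including any delay limit, and cross-refer between them.
4. In the compliance report, tabulate diarrhea-related cisplatin holds, reductions and omissions by arm, where the reason for the change is recorded.

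The first three items are a wording amendment. Their reach is limited by timing: Section 13.5 expects accrual to end around March 2017, Section 13.6.3 expects concurrent therapy to end around July 2017, and Section 7.9 already carries a date of 3/22/17. Few cisplatin doses would still be affected, though study drug continues for 3 months of maintenance. The table stays useful whenever the wording changes. Its cost depends on whether the Treatment Form captures reasons for holds. Section 12.1 names the form but does not show its content, so that needs checking first.

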APPENDIX V (Continued)

II. CTCAE v. 4 grade 4

1. Patient must call physician immediately for any Grade 4 diarrhea event
2. Discontinue treatment with lapatinib, hold chemotherapy (if applicable)
3. If loperamide has not been initiated, initiate loperamide immediately: Initial dose 4mg followed by 2mg every 2 hours or after every unformed stool
4. For dehydration use intravenous fluids as appropriate, if patient presents with severe dehydration administer octreotide
5. Perform stool work-up, CBC, electrolyte and other tests as appropriate
6. Recommend consulting with GI specialist
7. Administer antibiotics as needed (example fluoroquinolones), especially if diarrhea is persistent beyond 24 hours or there is fever or Grade 3/4 neutropenia
8. Supportive care and other intervention should be continued until diarrhea free (i.e., <Grade 1/bowel patterns returned to baseline) for 24 hours
9. Intervention may require hospitalization for patients most at risk for life threatening complications

Refer to and follow the recommended supportive care guidelines in the previous sections and as depicted in Figure 1 (see next page).

Figure 1: Algorithm for the management of diarrhea in patients treated with lapatinib-based therapy

1. For Grade 1 diarrhea that persists for 2 weeks or longer, refer to Section III.
2. For Grade 2 diarrhea that persists longer than 3 days/72 hours, refer to Section III.
3. For recurrent diarrhea, refer to Section IV for further management guidelines.

APPENDIX VI (2/2/16)

PROHIBITED MEDICATIONS

Lapatinib is a substrate for CYP3A4. Inducers and inhibitors of CYP3A4 may alter the metabolism of lapatinib. The following list of CYP3A4 inducers and inhibitors are prohibited from screening through discontinuation from study.

Drug Class	Specific Agents	Wash-out ¹
CYP3A4 Inducers		
rifamycin antibiotics	rifampicin, rifabutin, rifapentine	2 weeks
anticonvulsants	phenytoin, carbamazepine, barbiturates (e.g., phenobarbital)	
antiretrovirals	efavirenz, nevirapine, tipranivir, etravirine	
glucocortical steroids (oral only) Note: Steroids are required as an anti-emetic for cisplatin. The short-term administration of steroids for this indication poses minimal risk related to CYP3A4.	cortisone (>50 mg), hydrocortisone (>40 mg), prednisone or prednisolone (>10 mg), methylprednisolone or triamcinolone (>8 mg), betamethasone or dexamethasone (>1.5 mg) ²	
other	St. John's Wort, modafinil	
CYP3A4 Inhibitors		
antibiotics	clarithromycin, erythromycin, troleandomycin, flucloxacillin	1 week
antifungals	itraconazole, ketoconazole, fluconazole (>150 mg daily), voriconazole	
antiretrovirals	delaviridine, nelfinavir, amprenavir, ritonavir, indinavir, saquinavir, lopinavir, atazanavir	
calcium channel blockers	verapamil, diltiazem	
antidepressants	nefazodone, fluvoxamine	
gastrointestinal agents ³	cimetidine	
fruit juices	grapefruit, star fruit, and papaw	
other	amiodarone	6 months
Miscellaneous		
antacids	Mylanta, Maalox, Tums, Rennies	1 hour before and after dosing
herbal supplements ⁴	ginkgo biloba, kava, grape seed, valerian, ginseng, echinacea, evening primrose oil	2 weeks

-
1. Time period between last dose of listed drug and first dose of lapatinib, required to avoid drug-drug interaction potential for toxicity (inhibitors) or loss of efficacy (inducers) that could make the patient unevaluable. Clinically appropriate substitution of drugs not on the list is recommended.
 2. A standard 3-5 day course of dexamethasone at a dose following the institutions standard of care for the prevention and/or treatment of platinum-induced nausea and vomiting is allowed. Glucocortical steroid oral dose equivalents (in parentheses) to dexamethasone 1.5 mg (or less) given daily are allowed. Intravenous dosing should be considered if clinically appropriate.
 3. Emetogenic chemotherapy may require 3-4 daily doses of aprepitant. CYP3A4 inhibition by oral (not IV) aprepitant may require a concurrent dose reduction of 1-2 lapatinib tablets.
 4. This list is not all-inclusive; therefore, for herbal supplements not listed, please contact a Novartis Medical Monitor or Clinical Scientist.

NOTE: If future changes are made to the list of prohibited medications, formal documentation will be created and stored with the study file. Any changes will be communicated to the investigative sites in the form of a letter.

